### 9.3.2 Secondary Variables

- 
- Type of treatment regimen (± Dasabuvir, ± RBV, intended and actual combination, dose and duration)
- Patient adherence
- Serious and non-serious adverse events and pregnancy occurrences
- Questionnaire scores on PROs: Chronic Illness Therapy-Fatigue (FACIT-F), Work Productivity and Activity Impairment (WPAI), Burden of Suffering (PRISM), Patient Activation Measure (PAM-13)
- Co-morbidities and concomitant medication
- HCV relapse or reinfection after achieving SVR12 until post treatment week 48

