### 9.7.3.3 Statistical Methods for Analysis of Effectiveness Variables

The simple percentage of patients achieving SVR12 will be calculated and a two-sided 95% confidence interval (CI) of the percentage based on the Wilson's Score method will be computed.

Corresponding methods will be used for other response rates (EoT response rate, relapse rate, viral breakthrough). The relapse rates will be estimated in patients of the CP analysis groups with EoT response and sufficient HCV RNA measurements post-treatment. Viral breakthrough rates will be estimated in all patients of the CP analysis groups, who have at least one undetectable HCV RNA measurement on-treatment and at least one on-treatment or EoT measurement thereafter.

Univariate and multiple logistic regression (MLR) methods will be used to investigate the impact of the following explanatory covariates on SVR12:

- Key demographic information
- Mode of CHC infection
- HCV RNA level at baseline
- Most recent stage of liver fibrosis
- HCV genotype and subtype (if available)
- Type of treating institute
- Liver and/or CHC related co-morbidities
- Key clinical chemistry and hematology laboratory variables at baseline
- In treatment experienced patients only:
  - Most recent prior treatment for CHC
  - Outcome of most recent prior CHC treatment

Further details and additional covariates will be specified in the SAP.

These analyses will be of exploratory nature, data driven, and will be repeatedly performed for the CP. Backward selection procedures will be applied to generate the final MLR models which consider only covariates for which the percentage of patients with available data is greater than 80% of the patient group analyzed. A p-value <0.05 will be used for the covariates to stay in the model in a backward elimination step. Logistic

---

Confidential Information

regression methods will also be used to investigate the impact of treatment adherence on SVR12.

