**Core Population with Sufficient Follow-up [CPSFU {12, 24, 48}]**

In addition, the core population with sufficient follow-up data regarding SVR12, SVR24 or SVR48, respectively, is defined as all CP patients,

- who have evaluable HCV RNA data  $\geq 70$  days,  $>126$  days or  $>210$  days, respectively, after the last actual dose of the ABBVIE REGIMEN
- or a HCV RNA value  $\geq 50$  IU/mL at the last measurement post-baseline
- or had HCV RNA  $<50$  IU/mL at the last measurement post-baseline, but no HCV RNA measurement  $\geq 70$  days,  $>126$  days or  $>210$  days, respectively, after the last actual dose of the ABBVIE REGIMEN due to reasons related to safety (e.g. dropped out due to adverse event) or virologic failure (e.g. virologic failure such as relapse is reported in the electronic case report form (eCRF) but date and value of the corresponding HCV RNA test is missing).

This means only (1) patients who had virological response at their last on-treatment or post-treatment measurement, but had no post-treatment HCV RNA measurements  $\geq 70$  days,  $>126$  days or  $>210$  days, respectively, for reasons not related to safety or effectiveness (e.g. lost-to-follow-up or patient not willing to perform an additional HCV RNA test  $\geq 70$  days,  $>126$  days or  $>210$  days post-treatment, respectively) and (2) patients who had no post-baseline HCV RNA measurements for reasons not related to safety or effectiveness, and (3) patients with missing end of treatment date for reasons not related to safety or effectiveness, will be excluded from this analysis.

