#### 4.2.5 Patient Disposition

The frequencies of patients belonging to the different populations (i.e. EP, TP, CP, CPSFU; SP) will be summarized by genotype and cirrhosis status and overall using the EP analysis groups as specified in section 4.2.1. The reasons for exclusion from a particular population will be also summarized in the frequency tables. Additionally, information on patient disposition will be listed.

Furthermore the frequency of patients not completing the study as defined per protocol (i.e. no HCV RNA assessment performed at least 10 weeks post-treatment), will be summarized by treatment regimen and cirrhosis status and additionally by genotype and cirrhosis status and overall for the SP and CP. The reasons for not completing the study as entered on the CRF will be displayed (i.e. failure to return, insufficient virological response (HCV RNA detectable at end of treatment, relapse post-treatment), patient never started treatment, withdrawn consent, death, other).

Additionally, the main reason for early termination of the ABBVIE regimen (AE or SAE [Physician decision], virological non-response [Physician decision], rebound or breakthrough [Physician decision], resistance to DAA [Physician decision], patient refused to continue treatment, patient withdrew consent to participate in the study, lost to follow-up, other, unknown [if actual duration is shortened for more than 7 days]) and Ribavirin (Anemia, Nausea/Vomiting, Rash, Other) will be summarized by treatment regimen and cirrhosis status and additionally by genotype and cirrhosis status and overall for the following different analysis populations: CP and SP.

Finally the study regimens assigned at baseline will be summarized (a) by genotype and cirrhosis status and (b) by genotype and pre-treatment status (treatment naïve vs treatment experienced) for CP and SP.

An overview of tables is given in Table 7.

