##### 4.2.7.2 Secondary Variables

###### 4.2.7.2.1 Secondary Effectiveness Variables

###### Response

For the other response rates (i.e. RVR, SVR24 , SVR48, EoT response rate, relapse rate, viral breakthrough), the simple percentage of patients and a two-sided 95% confidence interval (CI) of the percentage will be computed (based on the Wilson's score method) as well. The RVR and EoT response rates will be reported for CP and the SVR24 and SVR48 rates will be reported for the respective CPSFU, stratified by genotype and cirrhosis status and overall. The relapse rates will be estimated stratified by SVR window (i.e. during SVR12 window=relapse12, during SVR24

window=relapse24, after SVR24 window=relapselate) and stratified by genotype and cirrhosis status and overall in patients of the CP with EoT response who fulfilled the following criteria:

- completed treatment as defined previously,
- had at least one HCV RNA measurement  $\geq 70$  days post-treatment or was a treatment failure between EoT and 70 days post-treatment.

Viral breakthrough rates [defined as at least one documented HCV RNA  $<50$  IU/mL followed by HCV RNA  $\geq 50$  IU/mL during treatment] will be estimated overall and stratified by genotype and cirrhosis status in all patients of the CP, who have at least one undetectable or unquantifiable, on-treatment HCV RNA measurement and at least one on-treatment or EoT measurement thereafter.

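### All three relapse windows share one day-70 entry criterion, so patients not tested later dilute the late relapse rates; relapse12 has no stated place for relapses seen only before day 70

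*SAP*

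**What the plan says.** SAP section 4.2.7.2.1 (Response) states: "The relapse rates will be estimated stratified by SVR window". It names relapse12 (in the SVR12 window), relapse24 (in the SVR24 window) and relapse-late (after the SVR24 window). SAP Table 3 puts these at days 70-126, days 127-210 and beyond day 210 after the last dose.

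The three rates are estimated "in patients of the CP with EoT response who fulfilled the following criteria". There are two criteria: completed treatment, and at least one HCV RNA value from day 70 on, unless the patient "was a treatment failure between EoT and 70 days post-treatment". No criterion is specific to a window. Each rate gets a Wilson interval, overall and by genotype and cirrhosis status.

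The same paragraph treats durability of response differently: "the SVR24 and SVR48 rates will be reported for the respective CPSFU". SAP section 4.2.1 makes that set window-specific: "the core population with sufficient follow-up data regarding SVR12, SVR24 or SVR48, respectively, is defined as all CP patients" with data from day 70 on, after day 126 or after day 210, or meeting one of the failure routes.

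Under SAP section 4.1.2 a relapse needs a value of at least 50 IU/mL following response at end of treatment. Protocol section 9.7.3.3 bases relapse on patients "with EoT response and sufficient HCV RNA measurements post-treatment". Protocol section 9.3.2 lists as a secondary variable: "HCV relapse or reinfection after achieving SVR12 until post treatment week 48".

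**The concern.** A cut-off at day 70 fits the first window only. A completer who tests negative on day 80 and is not seen again meets the entry criterion for all three rates. That patient cannot be a relapse24 or relapse-late event, because an event needs a measured positive value, and so is counted as relapse-free in windows nobody observed. A patient who relapsed on day 90 also stays in the later denominators, although no longer at risk of a first relapse.

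Empty late windows are to be expected. HCV RNA testing is left to the physician (SAP section 4.2.2). SAP section 4.2.5 defines not completing the study as "no HCV RNA assessment performed at least 10 weeks post-treatment", so one test at week 10 is enough to complete it. Late relapse is a named protocol variable, and its rate would look lower and more precise than the tests support.

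The second problem concerns relapse12. The entry criterion deliberately admits failures before day 70, yet the numerator is labelled by a window that opens on day 70. Such patients are foreseeable: post-treatment relapse is a listed reason for not completing the study (SAP section 4.2.5), and values from the start of a new HCV treatment are excluded (SAP section 4.2.3).

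**Working it through.** **Inputs.** From the documents: the windows (SAP Table 3), the entry criterion (SAP section 4.2.7.2.1), the Wilson method, and a subgroup size of 62 (SAP Table 1). Assumed, because the documents give no relapse or testing rates: 600 entrants, 18 relapses by day 126 (3.0%), hence 600 - 18 = 582 at risk later, and 40, 60 or 80% of those tested late.

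**Step 1, the plan's own figure.** The Wilson limits are [p + z²/2n ± z√(p(1-p)/n + z²/4n²)] / (1 + z²/n), with z² = 3.841. For p = 95%:
- n = 620: 92.99 to 96.46, width 3.47 (stated 3.5)
- n = 590: 92.93 to 96.49, width 3.55 (stated 3.6)
- n = 62: 86.49 to 98.26, width 11.77 (stated 11.8)

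All three rows of SAP Table 1 reproduce.

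**Step 2, precision when no late relapse is seen.** This step assumes no late relapse rate, only a share tested. With zero events the Wilson upper limit is z²/(n + z²).

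| Denominator | Upper limit |
|---|---|
| 600 (SAP set) | 3.841/603.841 = 0.64% |
| 233 tested (40% of 582) | 3.841/236.841 = 1.62% |
| 349 tested (60%) | 3.841/352.841 = 1.09% |
| 466 tested (80%) | 3.841/469.841 = 0.82% |

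In a subgroup of 62 the limit prints as 3.841/65.841 = 5.8%. With 25, 37 or 50 of the 62 tested it would be 13.3, 9.4 or 7.1%.

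**Step 3, the point estimate.** Suppose 1.0% of tested patients relapse late, and testing is unrelated to relapse. The SAP rate is 582 × t × 1.0% / 600, where t is the share tested:
- t = 0.4: 2.33/600 = 0.39%
- t = 0.6: 3.49/600 = 0.58%
- t = 0.8: 4.66/600 = 0.78%

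**Step 4, selective testing.** Suppose tested patients relapse at twice the rate of untested ones, with 1.0% overall among the 582. The untested rate is u = 1.0%/(1 + t) and the tested rate is 2u.

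| t | SAP rate, 2u × t × 582/600 | Tested-only rate, 2u |
|---|---|---|
| 0.4 | 0.55% | 1.43% |
| 0.6 | 0.73% | 1.25% |
| 0.8 | 0.86% | 1.11% |

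The SAP rate is too low here, and the tested-only rate is too high by a similar amount.

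**Step 5, relapses before day 70.** Let e be the share of the 18 relapses first seen before day 70, and v the share of those with no later usable value. The literal relapse12 numerator loses 18 × e × v:
- e = 0.3, v = 0.5: 2.7 lost, and (18 - 2.7)/600 = 2.55%
- e = 0.5, v = 1: 9 lost, and (18 - 9)/600 = 1.5%

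The rate with all relapses through day 126 counted is 18/600 = 3.0%.

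**The case against.** - **The split may only be a breakdown by timing over one denominator.** That is a possible reading. But the SAP calls these rates and gives them confidence intervals, without that label or the number tested. The table shells (Part II of the SAP) are not in the documents and could hold denominators, so the point rests on the SAP text alone.
- **The missing-as-failure rule in SAP section 4.2.3 may cover untested patients.** Applied to relapse, it would turn them into relapsers: with 60% tested, (582 - 349)/600 = 38.8% before any true event. The relapse definition requires a measured value, so the documents do not support this reading.
- **A tested-only rate can be biased too.** This stands (step 4). It argues for showing both rates and the number tested.
- **SVR24 and SVR48 already describe late durability.** They do, on follow-up-based sets. That does not correct the relapse rates beside them.

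A reader might infer more than the text supports:
- **That early relapses vanish from the report.** They do not. The Relapse category in the non-response table counts any positive value after end of treatment in completers, and these patients remain SVR12 failures. Only the three window rates can miss them.
- **That the SAP departs from the protocol.** The protocol does not define sufficient measurements for relapse. Its one definition of sufficient follow-up (section 9.7.1) also uses day 70, plus failure routes.
- **That imputed end-of-treatment status biases relapse.** The SAP does not say whether observed or imputed response defines the relapse set. Backward imputation at end of treatment is in the protocol (section 9.7.1), and its net effect here may be nil. This is a matter for clarification only.

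**Conclusion.** The concern holds for two stated rules. First, the common entry criterion keeps patients without a late test, and patients who have already relapsed, in the relapse24 and relapse-late denominators. The resulting rates cannot exceed the true late rate except by chance, and their intervals claim information from patients who gave none. Under the assumptions above, a 1.0% late rate would read 0.39 to 0.78%, and a zero-event upper limit would be understated by a factor of about 1.3 (0.82/0.64) to 2.5 (1.62/0.64). Second, read literally, the relapse12 numerator leaves out relapses seen only before day 70, although the denominator admits those patients; in the example the rate falls from 3.0% to between 1.5 and 2.55%.

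The direction follows from the text. The size depends on testing shares and relapse rates that the documents do not give. The rates are secondary and descriptive, and primary SVR12 is untouched. A correction before the final analysis is worthwhile because the error favours the regimen and needs no new data to remove.

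**What to change.** 1. Report relapse24 among patients relapse-free through day 126 who have an HCV RNA value after day 126, with no upper limit on that value, as in the SVR24 follow-up set. Report relapse-late among patients relapse-free at their earlier tests who have a value after day 210. Assign each relapse to the window of its first value of at least 50 IU/mL.
2. For each window, give the number at risk and the number tested. Keep the all-entrants denominator as a labelled sensitivity analysis, and note that the tested-only rate may be too high if testing is selective.
3. State that relapse12 counts any HCV RNA value of at least 50 IU/mL after end of treatment through day 126.
4. State whether observed or imputed response at end of treatment defines the relapse set.
5. Align the Part II table shells with this wording.

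The cost is SAP wording and re-programming of the relapse table. The late denominators become smaller and their intervals wider, and selective testing may bias the new main rates upward, which is why both versions should be shown.

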### **Non-Response**

In another table, the numbers and the percentages of the SVR12 non-responder categories and responder will be summarized for CP patients, overall and stratified by genotype and cirrhosis status. The following SVR12 non-response categories will be considered:

- On-treatment virologic failure (breakthrough [defined as at least one documented HCV RNA  $<50$  IU/mL followed by HCV RNA  $\geq 50$  IU/mL during treatment] or failure to suppress [each measured on-treatment HCV RNA value  $\geq 50$  IU/mL])
- Relapse (defined as HCV RNA  $<50$  IU/mL at EoT followed by HCV RNA  $\geq 50$  IU/mL post-treatment and completed treatment as defined previously)
- Death and none of the above
- Premature study drug discontinuation with no on-treatment virologic failure and none of the above
- Insufficient virological response, other than those mentioned above (patients for whom insufficient virological response was reported, or who had HCV RNA  $\geq 50$  IU/mL post EoT) and none of the above
- Missing SVR12 data and/or none of the above criteria

Virological response rates and non-response categories will be displayed for patients who completed treatment with ABBVIE regimen, as well.

### **SVR12 (Exploratory Analyses)**

Univariate and multiple logistic regression (MLR) methods will be used to investigate the impact of various explanatory covariates (patient and disease characteristics) at baseline on SVR12.

These analyses will be of exploratory nature, data driven, and will be performed for CP population. Univariate logistic regression will be performed first and then backward selection procedures will be applied to generate the final MLR model. A p-value  $<0.05$  will be used for the covariates to stay in the model in a backward elimination step. If the percentage of patients with available data for a variable is lower than 80% of the patient group analyzed, then this variable will not be considered in the MLR analysis.

The variables to be considered are as follows:

- Key demographic information
  - Age (continuous)
  - Gender (Female [reference], Male)
  - Race/ethnic origin (White/Caucasian [reference], Black, Asian/Oriental, Other [all other races]); at least two categories with at least 10% of the patients each have to exists, so that this variable will be considered
  - Weight (continuous)
  - BMI (continuous)
  - IL28B, rs12979860 (CC [reference], CT or TT); patients with unknown genotype are excluded from the respective analyses.
- CHC disease characteristics
  - Years since diagnosis (continuous)
  - Mode of CHC infection (Drug use [reference], Other [all other answers excluding unknown], unknown);
  - Most recent stage of liver fibrosis (No cirrhosis/Transition to cirrhosis [reference], Cirrhosis; for definition see 4.2.6.2);
  - HCV RNA level at baseline ( $\log_{10}$  IU/mL)
  - HCV genotype (G1a\*, G1b, G4; for definition see section 4.2.6.2)
  - Type of treating institute (Private Practice / Private Hospital, Academic / University Hospital, General Hospital, Other)
  - Co-infections (every patient not reporting the respective co-infection is considered as not having the respective co-infection)
    - HIV (No [reference], Yes)
    - HBV (No [reference], Yes)
  - Liver and/or CHC related co-morbidities (every patient not reporting the respective co-morbidity is considered as not having the respective co-morbidity)
    - Liver transplantation (No [reference], Yes)
    - Steatosis (non-alcoholic) (No [reference], Yes)
    - Decompensated liver disease (No [reference], Yes)
  - Other co-morbidities (every patient not reporting the respective co-morbidity is considered as not having the respective co-morbidity)
    - Depression (No [reference], Yes)
    - Diabetes mellitus (No [reference], Type 1/Type 2)

- Hypertension (No [reference], Yes)
- Immunologically mediated disease (No [reference], Yes)
- Hypothyroidism (No [reference], Yes)
- Alcohol use (None [reference], Yes –occasional, Yes –regular, Exdrinker)
- Key clinical chemistry and hematology laboratory variables at baseline
  - ALT ratio (continuous, see 4.2.6.5)
  - AST ratio (continuous, see 4.2.6.5)
  - Platelets [ $10^9/L$ ] (continuous)
- Prior treatment status (HCV treatment naïve [reference], HCV treatment experienced)

Additionally, an interaction term for cirrhosis status and genotype will be considered. If the most recent stage of liver fibrosis status (No cirrhosis/Transition to cirrhosis vs Cirrhosis), the genotype (G4, G1b vs G1a) or the interaction of both remains in the final model, then additional MLR might be considered for the subgroups concerned, taking into account the treatment regimen (e.g. in cirrhotic G1 patients: RBV vs no RBV and 12 wks vs 24 weeks).

The categories pre-specified above could be modified in the analyses if this is supported by the data (e.g. categories could be combined, if their impact on SVR12 is similar). Furthermore, continuous variables can be replaced by categorical variables.

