### **9.9 Limitations of the Research Methods**

The limitations of observational studies, such as uncontrolled confounding by lack of randomization, and difficulties to clearly interpret treatment effects in the context of missing data are well known. Their validity can be increased by accurate outcome measurements, documentation of the most common confounders, sufficient length of follow-up and by activities to obtain complete recording of available data as well as by searches for missing key data.

The most important outcome measure in this study is HCV RNA. Missing or unrecorded follow-up HCV RNA data can in particular lead to an underestimation of the real SVR rate as compared to the SVR rate of interventional trials. Highly sensitive and quantitative diagnostic tests are required to measure HCV RNA levels in blood. In an observational study each center will be using its own test – either commercially available or so-called “home-brew” tests – which might change from one visit to the next within a patient data set. The challenge is to accurately and consistently document test properties such as the LLoD and the ILLoQ to put the results into perspective of prior outcomes from

randomized controlled trials with (usually) central laboratory assessments for all trial participants.

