#### 4.2.3 Handling of missing data

No data will be imputed for any effectiveness or safety analyses except for the analyses of the HCV RNA endpoints and certain PRO endpoints. The discussion of missing data imputation for the PRO endpoints is included in section 4.2.7.2.3.

HCV RNA values will be selected for an RVR, EOTR and SVR analysis based on visit windows as defined in Table 4. When there is no HCV RNA value in a visit window based on defined visit windows, the closest values before and after the window, regardless of the value chosen for the subsequent and preceding window, will be used for the flanking imputation described below. For analysis of RVR, EOT and SVR, if a subject has a missing HCV RNA value at a post-Day 1 visit but with undetectable or unquantifiable (LLoD or LLoQ  $\leq$ 50 IU/mL) HCV RNA levels at both the preceding value and succeeding value, the HCV RNA level will be considered undetectable or unquantifiable, respectively, at this visit for this subject. In addition, if a subject has an

unquantifiable HCV RNA level at the preceding value and an undetectable HCV RNA level at the succeeding value, or vice versa, the HCV RNA level will be imputed as unquantifiable at this visit for this subject.

For analyses of RVR, subjects still missing a value for the visit after flanking imputation will be considered as a failure. For EoTR and SVR analysis, if there is no value in the appropriate window after flanking imputation but there is an HCV RNA value after the window, then it will be imputed into the EoTR or SVR window respectively. Subsequent to this flanking and backward imputation, if the HCV RNA value remains missing at a specific time point, then the subject will be considered as virological failure at this time point (i.e., not undetectable or unquantifiable).

If a subject starts another treatment for HCV, then all HCV RNA values for this subject measured on or after the start date of the new HCV treatment will be excluded from analyses. The subject will be considered a failure for summaries of viral response at all time points after the start of the new HCV treatment.

Due to the non-interventional nature of this study several different methods for determination of the HCV RNA value can be applied. For the purpose of the statistical analysis, a HCV RNA measurement is considered <50 IU/mL,

- if a PCR test was used

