### **Adherence**

Adherence will be displayed for the CP by genotype and cirrhosis status and for the SP by treatment regimen and cirrhosis status. Summary statistics (n, mean, median, standard deviation [SD], and range) will be generated for continuous variables. Numbers and percentages of patients will be presented for categorical variables.

- Adherence to ABBVIE regimen (% of target dose [adherence=cumulated number of pills taken /(initial prescribed number of pills x planned duration)])
  - >105%
  - >95%-<=105%
  - >80%-<=95%
  - >50%-<=80%
  - <=50%
- Adherence to ribavirin (% of target dose [adherence=cumulated dose taken /(initial prescribed dose x planned duration)])

- >105%
  - >95%-<=105%
  - >80%-<=95%
  - >50%-<=80%
  - <=50%
- Percentage of actual treatment duration in relation to the target duration of ABBVIE regimen taken
- Deviating duration of ABBVIE regimen
  - Early discontinuation (actual duration is shortened for more than 7 days)
  - Not deviated
  - Exceedance (actual duration is prolonged for more than 7 days)
- Method used to document adherence (Interview, Diary)
- Percentage of actual days with treatment with RBV in relation to the planned duration
- Ribavirin earlier discontinued than ABBVIE regimen
- Initial dose of Ribavirin
  - 1000 mg/day
  - 1200 mg/day
  - XXX
- Cumulative dose of Ribavirin (g)
- Dose modifications/termination of RBV [in patients taking RBV, for a patient more than one dose modification and its main reason could be reported, but for each single reason the patient is counted only once] (Total number of patients with lower dose than highest previous dose [including patients who stopped the treatment earlier], Anemia, Nausea/Vomiting, Rash, Other [including patients who discontinued ABBVIE regimen earlier, but did not stop the RBV treatment before the ABBVIE regimen])

In addition to the summary statistics of the adherence variables, logistic regression analyses will be performed for the following adherence variables: "adherence to ABBVIE regimen" in all patients of the CP, "adherence to ribavirin" in all patients of the CP taking RBV, each categorized as follows: >=95%, >80%-<=95%, <=80% to investigate the additional impact of overall treatment adherence on SVR12. The categories may be changed if they are sparsely filled. Adherence will be included as mandatory covariate in addition to the baseline explanatory variables already mentioned above. Also the same methods will be applied as described above.

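### The exploratory SVR12 predictor and adherence regressions run only in the core population, where unresolved missing SVR12 counts as failure; a side-by-side refit in CPSFU12 would show how far the odds ratios reflect missing follow-up

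*SAP*

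**What the plan says.** SAP section 2 lists predictive factors of virological response as a secondary objective. SAP 4.2.7.2.1, SVR12 (Exploratory Analyses), sets the population: "These analyses will be of exploratory nature, data driven, and will be performed for CP population". The procedure is: "Univariate logistic regression will be performed first and then backward selection procedures will be applied to generate the final MLR model". I count 27 candidate covariates plus one interaction term.

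Under Adherence, in the same section, two further logistic regressions are planned "to investigate the additional impact of overall treatment adherence on SVR12". One uses all CP patients, the other the CP patients taking ribavirin. Adherence is forced in and the other methods are unchanged. SAP Table 8 lists CP outputs only for all three models.

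SAP 4.2.3 fixes the outcome. If no value is available after flanking and backward imputation, "then the subject will be considered as virological failure at this time point".

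The CPSFU (SAP 4.2.1) sets aside patients whose last value showed response and who have no later test for reasons unrelated to safety or effectiveness. SAP 4.2.7.1 repeats the primary analyses in it. Under Response, "the SVR24 and SVR48 rates will be reported for the respective CPSFU". Interim response or non-response tables also use CPSFU12 (SAP 4.2.9.2 to 4.2.9.5). No regression does.

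Protocol 9.9 recognises the problem for the rate: "Missing or unrecorded follow-up HCV RNA data can in particular lead to an underestimation of the real SVR rate". It does not extend this to the regressions.

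**The concern.** Counting missing as failure is a fair composite for an effectiveness rate. In a regression read as evidence on virological response, it mixes two outcomes: the virus persisting or returning, and the patient not being tested. When virological failure is rare, a few untested patients can form a large share of the modelled events.

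Two errors can follow. A factor linked to attendance but not to virology can survive backward selection and be reported as a predictor. A true virological predictor unrelated to attendance is pulled toward an odds ratio of 1 and may drop out. SAP section 1 suggests that predictive factors found here could help optimise treatment, so the distinction has practical weight even in an exploratory analysis.

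**Working it through.** **The plan's own figures.** The Wilson score interval at 95% gives 92.99–96.46 (width 3.47) for n = 620, 92.93–96.49 (3.55) for n = 590 and 86.49–98.26 (11.77) for n = 62. These match SAP Table 1 to rounding. At 95% SVR12, the plan therefore expects 620 × 0.05 = 31 non-responders.

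**Inputs.** N = 620 is from SAP 3.2. The rest are assumptions, because the documents give neither a missing rate nor a link between covariates and attendance:
- virological failure v = 4%, independent of missingness;
- a covariate present in 20% with no virological effect;
- odds ratio R = 2 to 3 between covariate and being untested;
- overall share m with no HCV RNA value from day 70: 1%, 2%, 5% or 10%.

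With v = 4% and m = 1%, non-response is 0.01 + 0.99 × 0.04 = 4.96%, close to the plan's 5%.

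**CP formula.** Find m0 and m1 from 0.8·m0 + 0.2·m1 = m and m1/(1−m1) = R·m0/(1−m0). Then f = m_j + (1−m_j)·v in each group, and the CP odds ratio is [f1/(1−f1)]/[f0/(1−f0)].

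Example, m = 5%, R = 2: m0 = 0.0422 and m1 = 0.0811. So f0 = 0.0422 + 0.9578 × 0.04 = 0.0805 and f1 = 0.0811 + 0.9189 × 0.04 = 0.1178. The odds ratio is 0.1335/0.0875 = 1.52, although the covariate has no virological effect.

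**CPSFU12 formula.** Let a share k = 10% to 20% of untested patients stay in as failures (for example, untested for safety reasons). Then h = [k·m_j + (1−m_j)·v]/[k·m_j + 1 − m_j]. In the same example with k = 10%, h0 = 0.0442 and h1 = 0.0484, and the odds ratio is 1.10.

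**Dilution.** For a true odds ratio of 3 with 4% failure overall, v0 = 0.0293 and v1 = 0.0829. With equal missingness of 5% in both groups, f0 = 0.0778 and f1 = 0.1288, and the odds ratio is 1.75.

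**Results.** The untested share of events is m/[m + (1−m)·v]. Expected events are 620·[m + (1−m)·v] in the CP and 620·[k·m + (1−m)·v] in CPSFU12.

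| Missing m | Untested share of CP events | Spurious OR, CP (R = 2 / 3) | Spurious OR, CPSFU12 | True OR 3 as seen in CP | Events, CP to CPSFU12 |
|---|---|---|---|---|---|
| 1% | 20% | 1.17 / 1.31 | 1.02–1.07 | 2.50 | 31 to 25–26 |
| 2% | 34% | 1.30 / 1.54 | 1.04–1.14 | 2.20 | 37 to 25–27 |
| 5% | 57% | 1.52 / 1.98 | 1.10–1.32 | 1.75 | 55 to 27–30 |
| 10% | 74% | 1.70 / 2.34 | 1.19–1.58 | 1.46 | 84 to 28–35 |

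With a weaker link (R = 1.5), the CP odds ratio is 1.09, 1.16, 1.27 and 1.36. At 5% missing and R = 2 to 3, it is 1.69–2.31 if v = 2% and 1.42–1.78 if v = 6%.

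**What the planned outputs already show.**
- Final analysis, SAP 4.2.5: patients with "no HCV RNA assessment performed at least 10 weeks post-treatment" are tabulated with reasons, by genotype, regimen and cirrhosis.
- Final analysis, SAP 4.2.7.2.1, Non-Response: a missing-data row by genotype and cirrhosis. As worded, an untested early stopper fits "Premature study drug discontinuation with no on-treatment virologic failure and none of the above" before that row. The same section and Table 8 add tables restricted to treatment completers, which partly separates missing data from early stopping.
- Interim analyses: response or non-response tables repeated by age (SAP 4.2.9.2 to 4.2.9.4) and shown by opiate substitution (4.2.9.2 to 4.2.9.5). Comparing CP and CPSFU12 numbers by level gives a partial view. Opiate substitution is a covariate only in the interim models.

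Most of the 27 candidates, for example mode of infection, alcohol use, depression and institution type, have no such breakdown. Nor do the adherence categories.

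**The case against.** The strongest reply is that this is a choice of estimand. The models target SVR12 as the study defines it, and Protocol 7.2 describes effectiveness research as open to patient, provider and system factors. A factor that lowers documented cure through poor attendance is then a legitimate finding. This stands, and it is why the CP models should remain the main analysis. It does not settle the stated objective, which concerns virological response.

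The models are also secondary and labelled exploratory, and imputation rescues patients with a later test, so only residual missing values matter. Both points stand and lower the severity.

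A reader might infer three stronger things that the documents do not support:
- **That no planned output shows missing follow-up beyond genotype and fibrosis stage.** The interim tables by age and opiate substitution, and the completer-only tables, give part of the picture.
- **That untested early stoppers are simply hidden in the non-response table.** The completer-only version partly separates them, although it is not a breakdown by adherence category.
- **That CPSFU12 would give unbiased odds ratios.** It selects on post-baseline outcome and still counts some untested patients as failures.

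**Conclusion.** The gap is real and of low severity. All three regressions are CP-only, unresolved missing SVR12 counts as failure, and no CPSFU12 refit is planned. Their odds ratios may therefore partly reflect missing follow-up when read as predictors of virological response.

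The size depends on a missing rate that the documents do not give. Under the stated assumptions, the spurious odds ratio is modest at 1% missing (1.2–1.3), 1.3–1.5 at 2%, 1.5–2.0 at 5% and 1.7–2.3 at 10%. A true odds ratio of 3 shrinks to 2.5, 2.2, 1.75 and 1.5. CPSFU12 reduces the spurious odds ratio to 1.0–1.1 at 1–2% missing, 1.1–1.3 at 5% and 1.2–1.6 at 10%, but does not remove it.

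A reader might go on to conclude that the primary SVR12 rate is unsound or that the reported predictors will be artefacts. Neither follows. The composite is suitable for the rate, which has its own CPSFU sensitivity analysis. If follow-up is nearly complete, the two sets of odds ratios should largely agree.

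**What to change.** Keep the CP regressions as the main analysis, as Protocol 9.7.3.3 specifies. Before the final analysis, add to SAP 4.2.7.2.1:

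> As a sensitivity analysis, the final CP models (predictor, adherence to ABBVIE regimen, adherence to ribavirin) will be refitted in the CPSFU12 with the same covariates and categories and without new backward selection. Odds ratios with 95% CIs will be shown side by side with those of the CP. The number of CP non-responders with no HCV RNA value from day 70 onward will be shown by level of each covariate in the final models and by adherence category.

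Describe differences between the two sets of odds ratios. Do not add a numerical flag for how far an odds ratio must move, because any cut-off would be arbitrary.

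State the limits of CPSFU12: it selects on post-baseline outcome, still counts safety-related missing values as failures, reduces but does not remove the bias, may bias adherence in either direction, and cannot recover a predictor already diluted out of the CP model.

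The cost is SAP wording, three refits and one count table; CPSFU12 is already defined and used. The downside is fewer events (about 55 falling to 27–30 at 5% missing, under the assumptions) and wider intervals. This will be most marked in the ribavirin adherence model, which uses only patients taking ribavirin.
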